9.2 Institutional Review Board (IRB) Approval and Consent

It is expected that the IRB will have the proper representation and function in accordance with federally mandated regulations. The IRB must approve the consent form and protocol.

In obtaining and documenting informed consent, the investigator should comply with the applicable regulatory requirement(s), and should adhere to Good Clinical Practice (GCP) and to ethical principles that have their origin in the Declaration of Helsinki.

Before recruitment and enrollment onto this study, the subject will be given a full explanation of the study and will be given the opportunity to review the consent form. Each consent form must include all the relevant elements currently required by the FDA Regulations and local or state regulations. Once this essential information has been

provided to the subject and the investigator is assured that the subject understands the implications of participating in the study, the subject will be asked to give consent to participate in the study by signing an IRB-approved consent form.

Prior to a patient's participation in the trial, the written informed consent form should be signed and personally dated by the subject and by the person who conducted the informed consent discussion.

9.3 Required Documentation (for multi-site studies)

Not applicable

9.4 Registration Procedures

Not applicable

9.5 Data Management and Monitoring/Auditing

Trial monitoring will be conducted by no less than annually and refers to a regular interval review of trial related activity and documentation performed by the study team, which includes but is not limited to accuracy of case report forms, protocol compliance, timeliness and accuracy of Velos entries and AE/SAE management and reporting. Documentation of trial monitoring will be maintained along with other protocol related documents and will be reviewed during internal audit.

Toxicity and dose escalation reviews will be performed by the primary investigator, [name] at each follow up visit. These reviews will be documented in the visit note and electronic medical record.

9.6 Adherence to the Protocol

Except for an emergency situation in which proper care for the protection, safety, and well-being of the study subject requires alternative treatment, the study shall be conducted exactly as described in the approved protocol.

9.6.1 Exceptions (also called single-subject exceptions or single-subject waivers): include any departure from IRB-approved research that is *not due to an emergency* and is:

- intentional on part of the investigator; or
- in the investigator's control; or
- not intended as a systemic change (e.g., single-subject exceptions to eligibility [inclusion/exclusion] criteria)

➤ **Reporting requirement:** Exceptions are non-emergency deviations that require **prospective** IRB approval before being implemented. Call the IRB if your request is urgent. If IRB approval is not obtained beforehand, this constitutes a major deviation.

9.6.2 Emergency Deviations: include any departure from IRB-approved research that is necessary to:

- avoid immediate apparent harm, or
- protect the life or physical well-being of subjects or others

➤ **Reporting requirement:** Emergency deviations must be promptly reported

to the IRB within 5 working days of occurrence.

- 9.6.3 Major Deviations** (also called **violations**): include any departure from IRB-approved research that:
- Harmed or placed subject(s) or others at risk of harm (i.e., did or has the potential to negatively affect the safety, rights, or welfare of subjects or others), or
 - Affect data quality (e.g., the completeness, accuracy, reliability, or validity of the data) or the science of the research (e.g., the primary outcome/endpoint of the study)
 - **Reporting requirement:** Major deviations must be promptly reported to the IRB within 5 working days of PI awareness.
- 9.6.4 Minor Deviations:** include any departure from IRB-approved research that:
- Did not harm or place subject(s) or others at risk of harm (i.e., did not or did not have the potential to negatively affect the safety, rights, or welfare of subjects or others), or
 - Did not affect data quality (e.g., the completeness, accuracy, reliability, or validity of the data) or the science of the research (e.g., the primary outcome/endpoint of the study)
 - **Reporting requirement:** Minor deviations should be tracked and summarized in the progress report at the next IRB continuing review.

9.7 Amendments to the Protocol

Should amendments to the protocol be required, the amendments will be originated and documented by the Principal Investigator. A summary of changes document outlining proposed changes as well as rationale for changes, when appropriate, is highly recommended. When an amendment to the protocol substantially alters the study design or the potential risk to the patient, a revised consent form might be required.

The written amendment, and if required the amended consent form, must be sent to the IRB for approval prior to implementation.

9.8 Record Retention

Study documentation includes all Case Report Forms, data correction forms or queries, source documents, Sponsor-Investigator correspondence, monitoring logs/letters, and regulatory documents (e.g., protocol and amendments, IRB correspondence and approval, signed patient consent forms).

Source documents include all recordings of observations or notations of clinical activities and all reports and records necessary for the evaluation and reconstruction of the clinical research study.

Government agency regulations and directives require that the study investigator retain all study documentation pertaining to the conduct of a clinical trial. In the case of a study with a drug seeking regulatory approval and marketing, these documents shall be retained for at least two years after the last approval of marketing application in an International Conference on Harmonization (ICH) region. In all other cases, study documents should be kept on file until three years after the completion and final study report of this investigational study.

9.9 Obligations of Investigators

The Principal Investigator is responsible for the conduct of the clinical trial at the site in accordance with Title 21 of the Code of Federal Regulations and/or the Declaration of Helsinki. The Principal Investigator is responsible for personally overseeing the treatment of all study patients. The Principal Investigator must assure that all study site personnel, including sub-investigators and other study staff members, adhere to the study protocol and all FDA/GCP/NCI regulations and guidelines regarding clinical trials both during and after study completion.

The Principal Investigator at each institution or site will be responsible for assuring that all the required data will be collected and entered onto the Case Report Forms. Periodically, monitoring visits may be conducted and the Principal Investigator will provide access to his/her original records to permit verification of proper entry of data. At the completion of the study, all case report forms will be reviewed by the Principal Investigator and will require his/her final signature to verify the accuracy of the data.

11.0 APPENDICES

11.1 ThyTSQ

Treatment Satisfaction Survey

1. How satisfied are you with the current treatment for your underactive thyroid?

Very Dissatisfied	Dissatisfied		Neutral		Satisfied	Very Satisfied
0	1	2	3	4	5	6
						

2. How well do you feel the treatment is working?

Very Dissatisfied	Dissatisfied		Neutral		Satisfied	Very Satisfied
0	1	2	3	4	5	6
						

3. How convenient have you found your treatment to be recently (e.g. remembering to take the medication, getting prescriptions)?

Very Dissatisfied	Dissatisfied		Neutral		Satisfied	Very Satisfied
0	1	2	3	4	5	6
						

4. How satisfied are you with your understanding of your underactive thyroid?

Very Dissatisfied	Dissatisfied		Neutral		Satisfied	Very Satisfied
0	1	2	3	4	5	6
						

5. Would you encourage someone else with underactive thyroid to have your kind of treatment?

Very Dissatisfied	Dissatisfied		Neutral		Satisfied	Very Satisfied
0	1	2	3	4	5	6

Protocol SCCC-03315

						
-----------------------	-----------------------	-----------------------	-----------------------	-----------------------	-----------------------	-----------------------

6. How well do you feel that the treatment is controlling symptoms of underactive thyroid?

Very Dissatisfied	Dissatisfied		Neutral		Satisfied	Very Satisfied
0	1	2	3	4	5	6
						

7. How satisfied would you be to continue with your present treatment and dose?

Very Dissatisfied	Dissatisfied		Neutral		Satisfied	Very Satisfied
0	1	2	3	4	5	6
						

8. Are there any other features of your recent treatment for underactive thyroid, causing either satisfaction or dissatisfaction, that have **not** been covered by the questionnaire?

Yes	No
	

If yes, please describe:

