2.2 Secondary Objectives

- 2.2.1 To quantify the mean number of dose adjustments, and compare the two study agent group outcomes
- 2.2.2 To assess and compare quality of life differences between study groups using scores on QoL-Thyroid and ThyTSQ surveys

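### Four of the seven 0–6 items on the printed ThyTSQ form (2, 3, 5 and 6) carry satisfaction anchors that do not answer their question, most clearly item 5

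*Combined protocol and SAP*

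**What the plan says.** Section 2.2.2 makes a between-group comparison of quality of life a secondary objective, "using scores on QoL-Thyroid and ThyTSQ surveys". The Time and Events Table (section 5.2) schedules the ThyTSQ only at Visit 5 (weeks 17–19); at Visit 1 only the QoL-Thyroid is given.

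Appendix 11.1 reproduces the form. Items 1 to 7 each have seven boxes numbered 0 to 6 under the same labels, from Very Dissatisfied through Neutral to Very Satisfied. Item 8 is a yes/no question with free text. Three of the seven scaled stems ask about satisfaction: "How satisfied are you with the current treatment for your underactive thyroid" (item 1), "How satisfied are you with your understanding of your underactive thyroid" (item 4) and "How satisfied would you be to continue with your present treatment and dose" (item 7). The other four do not: "How well do you feel the treatment is working" (item 2), "How convenient have you found your treatment to be recently" (item 3), "Would you encourage someone else with underactive thyroid to have your kind of treatment" (item 5) and "How well do you feel that the treatment is controlling symptoms of underactive thyroid" (item 6).

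Neither the appendix nor section 8.3 says how a ThyTSQ score is formed or which items enter it.

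**The concern.** When the labels do not answer the question, the patient must guess what the number means. Someone who finds the regimen inconvenient but is content overall has no answer on item 3 that says so. Someone who would recommend the treatment although not satisfied with it has none on item 5. Patients will settle this in different ways, which adds noise. Many will probably fall back on how satisfied they are in general, which item 1 already asks, so the separate content of the four items is partly lost.

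Two features make this worth correcting in a small trial. The ThyTSQ is given once, so no later assessment can repair a poor reading. And the rationale in section 1.1 is better absorption and more predictable TSH. Items 2 and 6, on whether treatment works and controls symptoms, are the ThyTSQ items closest to that rationale, and both carry the ill-fitting row.

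**Working it through.** No figure in the plan can be reproduced here: the documents state no ThyTSQ score, range, variance or target difference. The check sets each stem in Appendix 11.1 against the row printed beneath it.

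| Item | Stem asks about | Printed row | Fit |
|---|---|---|---|
| 1 | satisfaction with treatment | satisfaction, 0–6 | yes |
| 2 | how well treatment works | satisfaction, 0–6 | loose: readable as satisfaction with effect |
| 3 | convenience | satisfaction, 0–6 | loose: readable as satisfaction with convenience |
| 4 | satisfaction with understanding of the condition | satisfaction, 0–6 | yes |
| 5 | whether the patient would encourage others | satisfaction, 0–6 | no |
| 6 | how well symptoms are controlled | satisfaction, 0–6 | loose: readable as satisfaction with symptom control |
| 7 | satisfaction with continuing | satisfaction, 0–6 | yes |

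Count: items 2, 3, 5 and 6 do not match, which is 4 of 7. Of these, one (item 5) clearly fails and three fit loosely.

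*Is it a fault of text extraction?* Probably not. The row is intact and identical under all seven items. The other questionnaire, in Appendix 11.2, changes its end labels with the question (difficulty, fear, size of problem, poor to excellent). One row under four differently worded stems in Appendix 11.1 therefore deserves a check for a copying slip.

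*In which direction does the error act?* All seven rows run from unfavourable (0) to favourable (6), so no item is reversed. Section 7.1 has both products encapsulated to keep the blind, and both arms complete the same form. The misfit therefore acts alike in both arms. It can blur a difference; it does not by itself create one.

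*How large is the noise?* It cannot be computed. The documents give no item-level variance or correlation.

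*How much data would a change of form split?* The plan has 10 completers per arm (section 8.2). If half had already reached Visit 5 (an assumption), each form version would hold 10/2 = 5 per arm. The possible range is 0 to 10 per arm on either version.

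**The case against.** The strongest reply is that the form is headed as a treatment satisfaction survey, so patients will take every item as asking how satisfied they are with the aspect named. For items 2, 3 and 6 that largely stands; the answers remain usable as ordered ratings. It does not rescue item 5, where being satisfied and being willing to recommend are different things.

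It is also fair to say that little depends on this. The ThyTSQ serves a secondary objective, the study is descriptive and not powered for testing, and section 8.3 promises caution with any test. That stands and sets the weight of the point.

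Some stronger readings are tempting, but the documents do not support them:

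- *That more than half of the satisfaction score cannot be interpreted.* This needs a total formed as an unweighted sum of items 1 to 7, which no section defines. Uninterpretable also does not follow from a count of loosely fitting labels that all run the same way.
- *That a real difference between formulations would be diluted by a known fraction.* This needs every item to carry equal signal, including item 4 on understanding of the condition, which has no evident link to capsule or tablet.
- *That the form departs from the published questionnaire, so its results cannot be set beside outside data.* The source is only cited (reference 9) and its anchors are not shown. No outside comparison is planned.
- *That convenience is a place where the products should differ.* Both are encapsulated and share the same intake instructions (sections 4.1 and 7.1).
- *That the lack of a baseline is a further flaw.* Satisfaction with a treatment cannot be asked before it starts, as the amendment summary notes.

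**Conclusion.** The point holds as a minor defect of the printed form. Four of seven scaled items carry anchors that do not match their question: item 5 clearly, items 2, 3 and 6 loosely. The expected harm is extra noise and overlap with item 1 in one secondary, once-only outcome. No bias between arms is shown, and the primary outcome (patients within the TSH target range) is untouched.

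The count rests only on the printed page. The judgement about noise and overlap assumes that patients differ in how they resolve the mismatch, which is plausible but not measured here. Whether the printed row is a copying slip or comes from the source cannot be settled from these documents.

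**What to change.** 1. Check the form in Appendix 11.1 against the source instrument (reference 9) and record the result.
2. Through an IRB modification, give items 2, 3, 5 and 6 response anchors that answer their stems. Keep the 0–6 numbering and the direction from unfavourable to favourable.
3. Add a form-version flag to the data.
4. Report all seven items individually, by arm and form version. Do not build a subset score from items 1, 4 and 7: nothing in the plan supports it, and it would keep the item on understanding of the condition while dropping effect and symptom control.
5. For patients assessed on the printed form, do not read item 5 as willingness to recommend.

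The cost is a one-page form, an IRB modification and one extra data field. The downside is two form versions among about 20 patients if some have already completed Visit 5, leaving few answers per arm on each. Reporting by item and version makes that visible but does not remove it.

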11.2 QoL-Thyroid

Quality of Life Scale/THYROID

Directions: We are interested in knowing how your experience of having thyroid cancer affects your quality of life. Please answer all of the following questions based on how you have been feeling **during the previous week**.

Physical Well Being

1. To what extent have the following been a problem during your illness and treatment?

a) Fatigue

no problem 0 1 2 3 4 5 6 7 8 9 10 **severe problem**

b) Appetite changes

no problem 0 1 2 3 4 5 6 7 8 9 10 **severe problem**

c) Aches or pain

no problem 0 1 2 3 4 5 6 7 8 9 10 **severe problem**

d) Sleep changes

no problem 0 1 2 3 4 5 6 7 8 9 10 **severe problem**

e) Constipation

no problem 0 1 2 3 4 5 6 7 8 9 10 **severe problem**

f) Menstrual changes or fertility

no problem 0 1 2 3 4 5 6 7 8 9 10 **severe problem**

g) Weight gain

no problem 0 1 2 3 4 5 6 7 8 9 10 **severe problem**

h) Tolerance to cold or heat

no problem 0 1 2 3 4 5 6 7 8 9 10 **severe problem**

i) Dry skin or hair changes

no problem 0 1 2 3 4 5 6 7 8 9 10 **severe problem**

j) Voice changes

no problem 0 1 2 3 4 5 6 7 8 9 10 **severe problem**

k) Motor skills/coordination

no problem 0 1 2 3 4 5 6 7 8 9 10 **severe problem**

l) Swelling/fluid retention

no problem 0 1 2 3 4 5 6 7 8 9 10 **severe problem**

2. Rate your overall physical health:

extremely poor 0 1 2 3 4 5 6 7 8 9 10 **excellent**

Psychological Well Being Items

3. How difficult is it for you to cope with your disease and treatment?

not at all difficult 0 1 2 3 4 5 6 7 8 9 10 **very difficult**

4. How good is your quality of life?

Extremely poor 0 1 2 3 4 5 6 7 8 9 10 **excellent**

5. How much happiness do you feel?

none 0 1 2 3 4 5 6 7 8 9 10 **a great deal**

6. Do you feel like you are in control of things in your life?

None at all 0 1 2 3 4 5 6 7 8 9 10 **completely**

7. How satisfying is your life?

not at all 0 1 2 3 4 5 6 7 8 9 10 **completely**

8. How is your present ability to concentrate or to remember things?

extremely poor 0 1 2 3 4 5 6 7 8 9 10 **excellent**

9. How useful do you feel?

not at all 0 1 2 3 4 5 6 7 8 9 10 **extremely**

10. Has your illness or treatment caused changes in your appearance?

not at all 0 1 2 3 4 5 6 7 8 9 10 **extremely**

11. Has your illness caused changes in your self-concept (the way you see yourself)?

not at all 0 1 2 3 4 5 6 7 8 9 10 **extremely**

12. How distressing were the following aspects of your illness and treatment:

a) Initial diagnosis

not at all distressing 0 1 2 3 4 5 6 7 8 9 10 **very distressing**

b) Surgeries

not at all distressing 0 1 2 3 4 5 6 7 8 9 10 **very distressing**

c) Time since my treatment was completed

not at all distressing 0 1 2 3 4 5 6 7 8 9 10 **very distressing**

13. How much anxiety do you have?

none at all 0 1 2 3 4 5 6 7 8 9 10 **a great deal**

14. How much depression do you have?

none at all 0 1 2 3 4 5 6 7 8 9 10 **a great deal**

15. To what extent are you fearful of:

a) Future diagnostic tests

no fear 0 1 2 3 4 5 6 7 8 9 10 **extreme fear**

b) A second cancer

no fear 0 1 2 3 4 5 6 7 8 9 10 **extreme fear**

c) Recurrence of your cancer

no fear 0 1 2 3 4 5 6 7 8 9 10 **extreme fear**

d) Spreading (metastasis) of your cancer
no fear 0 1 2 3 4 5 6 7 8 9 10 **extreme fear**

Social Concerns

16. How distressing has your illness been for your family?
none at all 0 1 2 3 4 5 6 7 8 9 10 **a great deal**

17. Is the amount of support you receive from others sufficient to meet your needs?
none at all 0 1 2 3 4 5 6 7 8 9 10 **a great deal**

18. Is your continuing health care interfering with your personal relationships?
none at all 0 1 2 3 4 5 6 7 8 9 10 **a great deal**

19. Is your sexuality impacted by your illness?
none at all 0 1 2 3 4 5 6 7 8 9 10 **a great deal**

20. To what degree has your illness and treatment interfered with your employment?

a) Motivation to work
no problem 0 1 2 3 4 5 6 7 8 9 10 **severe problem**

b) Time away from work
no problem 0 1 2 3 4 5 6 7 8 9 10 **severe problem**

c) Productivity at work
no problem 0 1 2 3 4 5 6 7 8 9 10 **severe problem**

d) Quality of work
no problem 0 1 2 3 4 5 6 7 8 9 10 **severe problem**

21. To what degree has your illness and treatment interfered with your activities at home?

a) Driving a car
no problem 0 1 2 3 4 5 6 7 8 9 10 **severe problem**

b) Household chores
no problem 0 1 2 3 4 5 6 7 8 9 10 **severe problem**

c) Preparing meals
no problem 0 1 2 3 4 5 6 7 8 9 10 **severe problem**

d) Leisure activities
no problem 0 1 2 3 4 5 6 7 8 9 10 **severe problem**

22. How much isolation do you feel is caused by your illness and treatment?
none at all 0 1 2 3 4 5 6 7 8 9 10 **a great deal**

23. How much financial burden have you incurred as a result of your illness and treatment?
none at all 0 1 2 3 4 5 6 7 8 9 10 **a great deal**
